128 key staff will be scheduled to address problems. A video of RL-IPostC conduction with
129 BGC is recorded for interventionist training, reviewed in detail in the training modules.
130 Case studies illustrating potential problems in adhering to the study protocol and
131 blinding will be discussed. This will serve as a guide for training clinical site personnel
132 and will be updated periodically throughout the study as needed.

133 An Executive Committee will be organized and periodically distribute a set of
134 frequently asked questions and answers to the participating centers. Any queries
135 regarding the study procedures during the study period will be addressed by the
136 executive committee through calls or messages through Wechat.

137 4.6 Outcomes

138 The safety outcomes within 7 days, which are categorized as dosage-limiting toxicities
139 (DLTs), including the following criteria: 1) Malignant MCA infarction, defined by a
140 midline shift of ≥ 5 mm at the level of septum pellucidum, anisocoria due to herniation,
141 or death resulting from herniation; 2) Complications associated with ischemic
142 postconditioning intervention that necessitate treatment, including distal vascular
143 embolism, local arterial dissection and vascular spasm at the intervention site of the
144 ICA; 3) Serious adverse events (SAEs) that are causally linked to the intervention.

145 The efficacy outcome is defined by the reduction in infarction growth, measured as an
146 infarction growth < 10 mL from baseline to 72 hours post-intervention. Infarction
147 volume will be evaluated using automate software analysis, which assesses baseline

148 CTP defined by relative cerebral blood flow (rCBF) $<30\%$ and 72-hour diffusion-
149 weighted imaging (DWI) or CT hypodensity volume.

150 5 PARTICIPANT SELECTION

151 All subjects will undergo a neurological and clinical assessment, routine laboratory
152 blood test and baseline brain imaging. All these materials will be collected and
153 screened by site physician. This includes standard of care use of non-contrast CT/ CT
154 angiography/ CT perfusion. In order to track the potential for enrollment, screening
155 log is required. Potential embolic LVO-AIS within 24 h of symptom onset ready for
156 thrombectomy will be screened and signed informed consent if patients meet the
157 inclusion and exclusion criteria except the item 9 and 10 of inclusion criteria. Before

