158 patient enrollment, all collaborating centers will obtain approval from the local IRBs
159 or ethics committees which have access to all trial documents.

160 5.1 Inclusion and exclusion criteria

161 Inclusion Criteria:

- 162 ① Age ≥ 18 years
- 163 ② Presenting with symptoms consistent with acute anterior circulation ischemic
164 stroke
- 165 ③ Pre-stroke modified Rankin Score 0-1
- 166 ④ Baseline National Institute of Health Stroke Scale (NIHSS) score ≥ 6
- 167 ⑤ Endovascular treatment can be initiated (femoral puncture) within 24 hours
168 from stroke onset (stroke onset time is defined as last known well time)
- 169 ⑥ Occlusion of the intracranial internal carotid artery, or the middle cerebral
170 artery (MCA) (M1 or M2) and is the culprit artery

171 ⑦ Ischemic core volume is < 70 ml, mismatch ratio >1.8 and mismatch volume
172 is >15 ml as determined by CT perfusion imaging

173 ⑧ Embolism verified as the etiology of occluded artery

174 ⑨ Modified Thrombolysis in Cerebral Infarction Score (mTICI) of 2b or 3
175 achieved after endovascular thrombectomy.

176 ⑩ Time from CT perfusion to successful reperfusion < 2 hours

177 ⑪ Informed consent signed

178 Exclusion Criteria:

179 ① Stenosis ($\geq 50\%$) of the proximal MCA, internal carotid artery (ICA), or
180 common carotid artery (CCA) of the culprit artery

181 ② Presence of an ICA lesion that prevent the use of a balloon guide catheter

182 ③ Multiple vascular embolisms on different pathways (e.g., bilateral MCA
183 occlusions, or an MCA and a basilar artery occlusion)

184 ④ Previous ischemic stroke within the past 3 months

185 ⑤ Expected survival time of less than 6 months, precluding follow-up at 90 days
186 (e.g., patient with malignant tumor)

187 ⑥ Currently pregnant, mental disease, advanced hepatic or renal insufficiency,
188 severe heart failure

189 ⑦ Participation in other clinical trials that may confound the outcome
190 assessment of this trial

191 ⑧ Any other circumstances deemed inappropriate by the investigator for
192 inclusion in this trial

193 5.2 Criteria for removal

194 Patients shall be withdrawn from the study after enrollment if either of the following
195 protocol deviations occurs: (1) the RL-IPostC procedure is not initiated within 5
196 minutes after recanalization, or (2) the procedure is not completed as per the required
197 dosage. However, termination of RL-IPostC due to patient intolerance will not

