198 warrant withdrawal; such cases must be adjudicated by the Clinical Events Committee
199 (CEC) to determine if they constitute an RL-IPostC-related adverse event. All
200 withdrawal cases will be documented in the case report form (CRF) and preserved for
201 audit. Withdrawn patients will be excluded from the efficacy analysis.

202 5.3 Criteria for drop out

203 All patients enrolled in the trial will be retained until the completion of the follow-
204 up. Subjects may request the withdrawal of informed consent and withdrawal from
205 this study at any time without any reason, and their medical rights will not be affected.
206 The investigator may also consider it medically necessary for the subject to
207 discontinue the study. For subjects who withdraw from the study, their reason for
208 withdrawal will be recorded, and the mRS score will be completed as far as possible
209 before withdrawal.

210 5.4 Criteria for discontinuation of clinical studies

211 This study will provide an optimal balance between safety and efficacy according to
212 pre-designed acceptable criteria, and the dosage will be abandoned or stopped once
213 unacceptable safety and efficacy criteria are met.

214 6 TREATMENTS

215 RL-IPostC procedure is administered immediately (within 5 minutes) following
216 revascularization. A balloon guiding catheter (BGC) is positioned at the ipsilateral C1
217 segment of ICA and is inflated and deflated to temporary stop antegrade blood flow.
218 This study examines six dosages levels, with the initial dosage set at Dosage
219 3(2min/2min, 4 cycles). The dosing schedule is as follows:

220 ① Dosage 1 (RL-IPostC 15/15, 5cycles): The intervention dosage consist of 15
221 seconds of occlusion followed by 15 seconds of reperfusion, repeated for 5 cycles.
222 ② Dosage 2 (RL-IPostC 60/60, 4 cycles): The intervention dosage consist of 60
223 seconds of occlusion followed by 60 seconds of reperfusion, repeated for 4 cycles.
224 ③ Dosage 3 (RL-IPostC 120/120, 4 cycles): The intervention dosage consist of 120
225 seconds of occlusion followed by 120 seconds of reperfusion, repeated for 4 cycles.
226 ④ Dosage 4 (RL-IPostC 180/180, 4 cycles): The intervention dosage consist of 180
227 seconds of occlusion followed by 180 seconds of reperfusion, repeated for 4 cycles.
228 ⑤ Dosage 5 (RL-IPostC 240/240, 4 cycles): The intervention dosage consist of 240
229 seconds of occlusion followed by 240 seconds of reperfusion, repeated for 4 cycles.

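### Section 5.2 withdraws patients from the study for a late or incomplete procedure, against 5.3's retention rule, and leaves 7-day DLT follow-up and counting of exposed patients unsecured

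*Protocol*

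**What the plan says.** Protocol 5.2 (Criteria for removal) states: "Patients shall be withdrawn from the study after enrollment if either of the following" of two deviations occurs. The first is that "protocol deviations occurs: (1) the RL-IPostC procedure is not initiated within 5" minutes of recanalization. The second is that the procedure is not completed at the required dosage. Stopping for patient intolerance is exempt and goes to the Clinical Events Committee for adjudication. The section ends: "Withdrawn patients will be excluded from the efficacy analysis". It does not mention safety analysis or later follow-up.

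Protocol 5.3 (Criteria for drop out) opens: "All patients enrolled in the trial will be retained until the completion of the follow"-up. The departures it then allows are the subject's own withdrawal and an investigator's medical decision. For those who leave, the mRS is sought before they go.

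Protocol 4.6 defines the toxicity endpoint: "The safety outcomes within 7 days, which are categorized as dosage-limiting toxicities". It includes malignant MCA infarction, intervention complications that need treatment, and SAEs causally linked to the intervention.

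The SAP's RDS table counts *evaluable* patients in #Pts, #Tox and #Eff and does not define the term. It has one #Pts column, with rows for 0, 5, 10, 15 and 20 patients only.

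**The concern.** A late start or a shortened procedure is a process deviation. It does not undo exposure to the occlusions already given. A patient who starts late and then receives the cycles, or who receives some of them, carries the risks that the DLT definition is meant to capture, and some of those events emerge over days. If such a patient leaves the study on the day of treatment, the DLT may never be observed. If it is observed, nobody can tell from the documents whether to count it.

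The second deviation deserves particular attention. If an operator stops because of a dissection or an embolism, and this is not classed as patient intolerance, the literal text removes the patient because of the toxicity itself. Removal would then be related to the outcome.

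At stake are the elimination of an over-toxic dosage (and with it all higher ones), the admissibility check when the optimal dosage is selected, and the 90-day mRS and SAE record of exposed patients.

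**Working it through.** **1. The two sections side by side.** 5.2 makes withdrawal from the study mandatory for a protocol deviation. 5.3 retains all enrolled patients, and its exceptions do not include protocol deviation. Nothing ranks one section above the other. The first trigger does not separate a patient who never received RL-IPostC from one who received it late. The second by its terms covers patients who may be partly exposed.

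**2. The plan's own boundaries.** Inputs: toxicity limit 0.15 and cutoff 0.95 (Protocol 4.1 and SAP), and an assumed Beta(1,1) prior. With k DLTs in n patients,

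Pr(πT > 0.15 | k, n) = P(Beta(1+k, 1+n−k) > 0.15) = P(Bin(n+1, 0.15) ≤ k).

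For 2/5: 0.3771 + 0.3993 + 0.1762 = 0.953, above 0.95. The smallest k that crosses the cutoff is 2 of 5 (0.953), 4 of 10 (0.984), 5 of 15 (0.976) and 6 of 20 (0.971). These are the RDS table's toxicity boundaries, so the assumed prior reproduces the plan.

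**3. One DLT at the boundary goes uncounted.** Without replacement, the patient leaves numerator and denominator. With replacement, a patient without a DLT takes the place.

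| Full count | Not replaced | Replaced, no DLT |
|---|---|---|
| 2/5: 0.953 | 1/4: 0.835, kept | 1/5: 0.776, kept |
| 4/10: 0.984 | 3/9: 0.95003, still just eliminated | 3/10: 0.931, kept |
| 5/15: 0.976 | 4/14: 0.938, kept | 4/15: 0.921, kept |
| 6/20: 0.971 | 5/19: 0.933, kept | 5/20: 0.917, kept |

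Three of four eliminations reverse without replacement, and all four with it. Neither document says which applies, and the RDS table has no rows for 4, 9, 14 or 19 patients.

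**4. Average effect if removal is unrelated to DLT.** Take a true DLT rate of 0.30 and, as an assumption, one removal per cohort of 5 without replacement. The limit is 2 events at n = 4 as well as at n = 5.

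- First cohort, 5 observed: 1 − 0.7⁵ − 5(0.3)(0.7⁴) = 1 − 0.168 − 0.360 = 0.472.
- First cohort, 4 observed: 1 − 0.7⁴ − 4(0.3)(0.7³) = 1 − 0.240 − 0.412 = 0.348.
- Two cohorts at the same dosage, 5+5 (limit 4 at n = 10): 0.472 + 0.168 × 0.031 + 0.360 × 0.163 = 0.536.
- Two cohorts, 4+4 (limit 3 at n = 8, posterior 0.966): 0.348 + 0.240 × 0.084 + 0.412 × 0.348 = 0.512.

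The first-cohort gap of about 12 points falls to about 2 after the second. With two removals per cohort, the two-cohort figure is 0.321, a much larger loss, but this assumes that 40% of patients are removed, for which the documents give no basis.

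**5. The opposite error.** Counting partly treated patients without a DLT as full-dosage exposure dilutes the rate. 3/9 meets the 0.95 rule (0.95003), whereas adding one such patient gives 3/10 (0.931), which does not.

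**The case against.** The tempting stronger reading is that 5.2 ends 7-day DLT observation in patients who had the full set of occlusions. The documents do not say so. The only analysis consequence in 5.2 is exclusion from efficacy, which suggests that safety still counts. Section 7.2 defines adverse events from consent to the last follow-up visit, and 10.2 requires a complete eCRF for every enrolled participant. A coherent reading exists in which such patients leave the efficacy analysis and stay for safety. Nor does any passage describe treatment after a late start. Section 6 gives the procedure within 5 minutes, and a late patient may receive no occlusions at all.

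A reader might also take the first-cohort fall from 0.47 to 0.35 as the size of the problem. It rests on no replacement, an assumed removal rate and one cohort, and it mostly shrinks by the second. If cohorts are filled to 5 evaluable patients and removal is unrelated to DLT, the figure stays at 0.47. De-escalation also gives protection short of elimination: 1/5 and 1/4 (0.20 and 0.25) both exceed λd = 0.179.

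Most of this stands, and it limits the claim. It does not remove the conflict. Sections 7.2 and 10.2 lean towards continued capture but do not settle it for a patient withdrawn from the study, and 5.3's wish for an mRS before withdrawal points the other way. If safety is meant to continue, 5.2 has to say so. De-escalation leaves a dosage that should have been eliminated, and those above it, open to later use or selection.

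**Conclusion.** The point holds as a conflict between two stated rules, with a gap in how exposed patients are followed and counted. Follow-up is not secured and may be ended on the plain words of 5.2. It cannot be said that the protocol ends it.

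The firm result is local: a single uncounted DLT at the boundary reverses elimination at 5, 15 and 20 patients without replacement, and at all four sample sizes if a patient without a DLT takes the place. This rests on the Beta(1,1) prior, which reproduces the plan's boundaries. The overall effect on operating characteristics cannot be stated. It depends on the removal rate, on replacement and on whether removal is related to DLT, and the documents specify none of these. The matter should be put right because safety drives the dose decisions and the correction is cheap.

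**What to change.** **Protocol 5.2 and 5.3.**
- Replace withdrawal from the study with exclusion from the efficacy analysis, which brings 5.2 into line with 5.3.
- State that every patient in whom at least one balloon occlusion was begun, under either trigger, stays in DLT follow-up to day 7 and in AE/SAE and mRS follow-up to day 90.
- State that any DLT in such a patient counts at the assigned dosage in Pr(πT > 0.15 | data).

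**SAP.**
- Define *evaluable* separately for toxicity and for efficacy, including where patients with no occlusion begun belong.
- State whether patients excluded from efficacy are replaced.
- State that the safety criterion is computed directly from the posterior when the toxicity and efficacy denominators differ, because the RDS table has a single #Pts column.
- State in advance whether a partly treated patient without a DLT enters the toxicity denominator, given the dilution shown above.

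**Cost.** A short SAP rule, a wording change in 5.2, and a few visits already in the flowchart. No change to the 5-minute rule or to any dosage is proposed.

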230 ⑥ Dosage 6 (RL-IPostC 300/300, 4 cycles): The intervention dosage consisted of 300
231 seconds of occlusion followed by 300 seconds of reperfusion, repeated for 4 cycles.

232 7 SAFETY

233 7.1 Adverse events and management of SAEs

234 All adverse events occurring during the trial must be truthfully recorded in the adverse
235 event table. The investigator should give targeted treatment and follow-up for adverse
236 events until symptoms disappear or symptoms stabilize. In cases of serious adverse
237 events, the investigator should take necessary treatment measures immediately to
238 protect the safety of the subject when informed of the case.

239 7.2 Definitions of adverse events and severe adverse events

240 Adverse events: Any adverse medical occurrence from the time the subject signed the
241 informed consent form to the last follow-up visit, regardless of whether there is a causal
242 relationship with the trial treatment, is considered an adverse event. Adverse events that
243 may occur during mechanical thrombectomy procedures usually include, but are not
244 limited to: (1) Allergic reactions, (2) Puncture point bleeding, (3) Thromboembolic
245 events, (4) Cerebral vasospasm, (5) Acute occlusion Possible causes, (6) Thrombosis
246 and plaque shedding, (7) Blood vessel rupture, (8) Cerebral hyperperfusion syndrome.

247 Serious adverse events: Events requiring hospitalization, prolonged hospitalization,
248 disability, affecting work capacity, endangering life or death, and causing congenital
249 malformations during clinical trials. The following hospitalizations are not considered
250 SAEs: Elective surgery already planned before signing the informed consent form;
251 routine physical examination; hospitalization due to medical procedures not planned by
252 the protocol; Elective admission to the hospital for stent implantation; Continued
253 hospitalization for the purpose of neurorehabilitation therapy only.

254 7.3 Relationship to study treatment

255 RL-IPostC operation related adverse events are judged by CEC, including but not
256 limited to distal vascular embolization within the territory, local arterial dissection, local
257 vasospasm of the internal carotid artery requiring treatment, and large infarction growth
258 due to delayed reperfusion. Treatment measures: Once the distal blood vessel embolism
259 is blocked, antiplatelet drugs should be used immediately, thrombectomy should be

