260 performed if necessary, local arterial dissection should be observed in light cases, and
261 stent implantation should be performed in severe cases.

262 7.4 AE Reporting

263 Once an adverse event (including serious adverse events) occurs, the time of occurrence
264 of the adverse event, clinical manifestations, treatment process and duration, outcome
265 and relationship with the drug should be recorded in detail on the case report form. If
266 there are abnormal laboratory tests, the patient must be followed until the test results
267 return to normal. Serious adverse events should be completed and reported to the
268 investigator, the Ethics Committee (EC)within 24 hours after being notified.

269 The CEC consists of three experts, two neurointerventionists and a neurologist. The
270 committee will assess all complications that occur during the course of the study and
271 classify the severity and relevance according to the definitions in the Adverse Events
272 (AEs) section. The CEC may request any relevant images and information required for
273 the AE determination.

274 8 STATISTICAL CONSIDERATIONS

275 8.1 Sample size estimates

276 This maximum sample size of 60 and 12 cohorts, with a sample size of 5 for each cohort.

277 8.2 Statistical analysis plans

278 Details in supplementary material of statistical analysis plans (SAP).

279 8.3 Data safety monitoring plan

280 The independent Data and Safety Monitoring Board (DSMB) is composed of
281 experienced two neurologists and one biostatistician who are neither directly involved
282 in the study. The DSMB meets before the study initiation and during the study as
283 required to reviews structured open-ended reports provided by research statisticians.
284 The DSMB is responsible for making recommendations to the Executive Committee on
285 the dosage escalation and deescalation, cessation or continuation of the study. In
286 addition, the DSMB will review the occurrence of SAEs and make recommendations
287 on the safety of the trial to continue, stop, or modify the study protocol.

288 9 ETHICAL AND REGULATORY STANDARDS

289 9.1 Ethical considerations

290 This clinical study must be conducted in accordance with the requirements of the
291 Declaration of Helsinki and other relevant regulations. Before the study begins, the
292 study protocol and informed consent form (ICF) and other documents must be approved
293 by the Ethics Committee of the research center before the study can be conducted.

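### Protocol 7.2 exempts hospital stays for procedures the protocol did not plan, so a complication that is serious only through hospital stay can miss SAE reporting

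*Protocol*

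**What the plan says.** Section 7.2 of the protocol first sets the seriousness criteria. Two concern hospital stay: "Serious adverse events: Events requiring hospitalization, prolonged hospitalization". The others do not: "disability, affecting work capacity, endangering life or death, and causing congenital" malformations.

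The section then introduces exclusions: "malformations during clinical trials. The following hospitalizations are not considered" SAEs. There are five: surgery already scheduled before consent, a routine examination, the item at issue, an elective stent admission, and a stay continued only for neurorehabilitation. The item at issue reads "routine physical examination; hospitalization due to medical procedures not planned by" the protocol.

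SAE status is used in three places:

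- **Expedited reporting (7.4, repeated in 9.1).** SAEs go to the Ethics Committee within 24 hours.
- **DSMB review (8.3).** "addition, the DSMB will review the occurrence of SAEs and make recommendations" on whether the trial continues, stops or is modified.
- **DLT item 3 (4.6).** The third DLT category is "ICA; 3) Serious adverse events (SAEs) that are causally linked to the intervention", with a 7-day window: "The safety outcomes within 7 days, which are categorized as dosage-limiting toxicities".

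**The concern.** Four of the five exclusions describe stays that are pre-arranged, routine, elective or purely rehabilitative, so none is prompted by an adverse event. The disputed item has no such limit. Its wording takes in an admission for an unplanned procedure to treat a complication, which is the kind of event an SAE definition is meant to catch.

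At stake is what the Ethics Committee hears within 24 hours and what the DSMB sees as SAEs. To a lesser degree, so is what counts under DLT item 3. Six sites apply this wording and could classify the same event differently.

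**Working it through.** This is mainly a comparison of texts. The arithmetic at the end only shows how sensitive the design is to one event.

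**1. Which events are exempt.** The exclusions in 7.2 apply to hospitalisations only.

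- A complication that endangers life, disables, affects work capacity or kills is an SAE, whatever procedure follows.
- A complication that meets only a hospital-stay criterion, where the stay is for a procedure the protocol did not plan, is exempt on the literal wording.
- A complication treated by thrombectomy or stent implantation is unclear. Section 7.3 names both as treatments for some RL-IPostC complications, and the protocol does not say whether naming them makes them planned.

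**2. Whether prolonged stays are covered.** The criteria separate hospitalisation from prolonged hospitalisation, and the disputed item uses only the first term. However, the last exclusion concerns a continued stay, so the list is not confined to new admissions. The text does not settle the point.

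**3. Whether another section restores the event.**

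- All adverse events go on the case report form (7.4), but that alone triggers no expedited report.
- The CEC assesses all complications, but classifies them by the definitions in the adverse event section, which contains the disputed item.
- The DSMB's role in dose recommendations (8.3) is not confined to SAEs, but its stated safety review is of SAEs.

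Nothing therefore returns an exempt event to the 24-hour report or the SAE review.

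**4. DLT exposure.** Item 1 (malignant MCA infarction) and item 2 (intervention-associated complications needing treatment) do not refer to SAE status. Item 2 introduces embolism, dissection and spasm as examples. A complication caused by the intervention and needing an operation also needs treatment, so on the ordinary reading it is a DLT under item 2. What remains exposed is an intervention-linked event within 7 days that is serious only through hospital stay and falls under neither item 1 nor item 2. If a site treated item 2 as a closed list of three, the exposed group would be larger.

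**5. Sensitivity to one event.** The formula is Pr(πT > 0.15 | x of n) = Pr(Beta(1 + x, 1 + n − x) > 0.15). The limit 0.15 and the cut-off 0.95 are in protocol 4.1 and the SAP. The Beta(1,1) prior is an assumption, supported by its reproduction of the elimination counts in eTable 1:

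| n | smallest x eliminated | posterior at x | posterior at x − 1 |
|---|---|---|---|
| 5 | 2 | 0.9527 | 0.7765 |
| 10 | 4 | 0.9841 | 0.9306 |
| 15 | 5 | 0.9765 | 0.9209 |
| 20 | 6 | 0.9713 | 0.9173 |

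In a first cohort of five, missing one DLT turns 2/5 (the dose and all higher doses eliminated) into 1/5 (not eliminated). The dose would still not be freely chosen: 1/5 = 0.20 exceeds the boundary 0.179. Assuming the flowchart, which is not shown, assigns Case C above that boundary, the next cohort goes down to dose 2, which is untried (RDS 262) and not marked E. Missing one DLT at 1/5 gives 0/5, which is below 0.118 and so Case A, where a higher dose becomes eligible.

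These figures hold for any missed DLT. They say nothing about how often this wording would cause one.

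**The case against.** The strongest reply is that dose finding is already protected. Items 1 and 2 of section 4.6 work without SAE status, the CEC looks at every complication, and the protocol synopsis lists other adverse events attributable to the procedure as a safety outcome separately from serious ones. This largely stands for DLT counting. It does not answer the loss of expedited reporting and SAE review.

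A second reply is that the disputed item may have been meant for admissions unrelated to the trial, or for new admissions only. Either is possible, but the text states neither limit.

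Three stronger readings are tempting, and the documents do not support them:

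- *Every unplanned operation for a complication drops out of the SAE count.* It does not, because the other seriousness criteria are untouched.
- *BOIN12 will materially under-count toxicity.* No RL-IPostC event is identified that clearly escapes items 1 and 2. Surgical repair of a puncture-site bleed is not such an event: 7.2 lists puncture bleeding as an event of mechanical thrombectomy, and it would count under item 3 only if linked to RL-IPostC.
- *Prolonged stay is usually the only criterion met, because every patient is in hospital for the first 7 days.* The documents state neither part.

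**Conclusion.** The point holds in a limited form. Section 7.2 contains a stated rule that, read literally, gives the wrong safety classification to a complication that is serious only through hospital stay and is treated by an unplanned procedure. The firm consequence is that such an event need not reach the Ethics Committee within 24 hours or enter the DSMB's SAE review. The effect on DLT counts is probably small and confined to item 3.

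The size cannot be estimated, because the documents give no frequency of such events. The conclusion rests on the literal wording and, for inpatients, on the exclusion reaching prolonged stays. The DLT part also rests on reading item 2 as open-ended.

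**What to change.** In section 7.2:

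- Limit the disputed exclusion to hospitalisations for procedures not prompted by an adverse event.
- Apply the same limit to the elective stent item.
- Add: *Any hospitalization required or prolonged to treat an adverse event, including by a procedure named in 7.3, is an SAE.*

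Simply reversing the phrase, so that it exempts procedures planned by the protocol, would not be safe. The thrombectomy and stent implantation that 7.3 names for RL-IPostC complications could then be called planned, and so exempt.

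Reconcile 7.2 with 4.6, 7.3, 7.4 and 8.3, and carry the wording into the case report form instructions. The cost is a text change and a few more SAE reports. The maximum of 60 patients, the boundaries (0.118, 0.179) and the RDS table stay as they are.
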